### **Responder Analysis**

The number and percentage of responders will be provided by treatment group. A subject who had as two consecutive ALT values within normal range during the treatment period will be defined as a responder. Subjects who are not responders and early withdraw will be considered as non-responders. Cochran-Mantel-Haenszel statistics will be provided adjusting for diabetes stratum.

```
*****  
Note:  
  TREATMENT = 0, (placebo), 1 (JKB-121 5 mg), 2 (JKB-121 10 mg)  
  DIABSTAT = nondiabetic, diabetic  
  RESPONDER: Y/N responder  
  COUNT: number of subjects  
*****;  
proc freq data=ALT;  
  tables DIABSTAT*TREATMENT*RESPONDER / cmh;  
  weight COUNT;  
run;
```

Sensitivity analyses will be conducted using subjects who complete the study.

Similar summaries and analyses will be provided for:

- Subjects whose ALT level at each scheduled visit during the treatment period is within normal range.
- Subjects whose ALT level is within normal range at any time within the following time intervals which will be derived using actual study days:
  - a. Baseline to Week 12

b. Week 12 to Week 24

- Subjects achieving a 20% reduction from baseline at any time during the treatment period.

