## 3 STUDY OBJECTIVES

### 3.1 Primary Objective

To evaluate the safety and potential efficacy of two dose levels of JKB-121 (5 mg twice daily and 10 mg twice daily) in reducing liver fat compared to placebo.

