#### ALT change from Baseline:

The current sample size of 20 subjects per group should yield approximately 73% power to detect a treatment effect of at least 30 U/L assuming a SE of 50 U/L ( $\alpha= 0.05$ ; two tailed; unpaired t-test). The SD of 50 U/L for the change from baseline endpoint was derived assuming SDs of 40 for the pre-and post-baseline measurements with a correlation of 0.25.

Sample size and power estimates have not been adjusted for multiple comparisons or multiple endpoints, dropouts or stratifications.

The analysis of each primary endpoint will be based on a linear model that incorporates the baseline measures as a covariate, the stratification factor and randomization treatment group. Pairwise comparisons of each active treatment group to control will be conducted vial linear contrasts.

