## 6.9 Efficacy Analysis

### 6.9.1 Primary Efficacy Endpoint

The change from baseline at Week 24 of the percentage fat content of the liver measured by MRI will be analyzed by analysis of covariance (ANCOVA) in the Full Analysis Set Population with treatment group and diabetes stratum as factors and baseline MRI value as a covariate. The comparisons will be (1) between the response of the JKB-121 5 mg group and the response of the Placebo group and (2) between the response of the JKB-121 10 mg group and the response of the Placebo group. The least-squares means, standard errors, and 95% confidence intervals for each treatment group and for each comparison will be provided. The two-sided p-values testing for significance within treatment group change from baseline and comparisons between treatment groups will be presented. No multiple comparisons techniques will be applied. The sample SAS code can be found below:

```
*****
Note:
  TREATMENT = 0, (placebo), 1 (JKB-121 5 mg), 2 (JKB-121 10 mg)
  DIABSTAT = nondiabetic, diabetic
  BASE: baseline percentage fat content of the liver measured by MRI
  CHG: change from baseline to Week 24 in the percentage fat content of
       the liver measured by MRI
*****;
proc glm data=MRI;
  class TREATMENT DIABSTAT;
  model CHG = TREATMENT DIABSTAT BASE / ss1 ss3;
  means TREATMENT;
  lsmeans TREATMENT / cov stderr pdiff cl;
  estimate "JKB-121 5 mg : Placebo" TREATMENT -1 1 0;
  estimate "JKB-121 10 mg : Placebo" TREATMENT -1 0 1;
run;
```

The data and model residuals will be inspected for normality and homogeneity of variance, and a logarithmic transformation will be applied if necessary.

To handle missing results such as due to early termination, multiple imputation will be performed. The detailed steps are specified below.

Step 1: Prepare the data for multiple imputation. Since there is only one intermediate visit (Week 12) for MRI collection, the missing pattern would be monotone if endpoint values are not available.

Step 2: PROC MI would be used to impute the missing MRI values. The treatment, diabetes stratum, and MRI values at baseline and all available post-baseline visits would be included. The SAS code can be found as below:

```
PROC MI data=MRI out=MI_OUT nimpute=1000 seed=12345 minimum=0;  
  var TREATMENT DIABSTAT BASE WEEK12 WEEK24;  
  mcmc initial=em prior=jeffreys nbiter=200 niter=500 chain=single;  
run;
```

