Step 3: Endpoint would be calculated by averaging the values of Week 12 and Week 24. For each imputation, the ANCOVA model specified above would be performed to compare the change from baseline to Week 24 endpoint between JKB-121 5 mg group the placebo group, and between JKB-121 10 mg group and the placebo group.

Step 4: The procedure PROC MIANALYZE would be used with estimated statistics (“least-squares means”) and associated standard error from each simulation for overall testing results. The overall least-squares means, standard errors, 95% confidence intervals, and p-values would be reported.

The same analysis will be repeated for the mITT and Per Protocol Populations. Multiple imputation will not be performed for the Per Protocol Population; only subjects with both baseline and endpoint will be included in the analysis.

The percentage of fat content of the liver measured by MRI at Baseline and Week 24 will be summarized descriptively, as well as the change from baseline.

The same descriptive statistics and ANCOVA model as the primary efficacy endpoint will be applied to the percentage of fat content of the liver measured by MRI at Baseline and Week 12.

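### The planned CMH test for the secondary ALT responder endpoints gives only three-arm statistics and no comparison of either dose with placebo

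*SAP*

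**What the plan says.** SAP 6.9.2.1, Responder Analysis, defines treatment with three levels, "TREATMENT = 0, (placebo), 1 (JKB-121 5 mg), 2 (JKB-121 10 mg"), and runs one PROC FREQ on them: "tables DIABSTAT*TREATMENT*RESPONDER / cmh". No WHERE or BY statement restricts the table to one dose and placebo. The accompanying text is "Cochran-Mantel-Haenszel statistics will be provided adjusting for diabetes stratum". It names no particular statistic, comparison, effect measure or interval. Counts and percentages of responders are promised by arm.

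The same form is reused for ALT within normal range at each scheduled visit, ALT within range at any time in two intervals, and a 20% fall from baseline. The normal-range analyses are done under two definitions of normal.

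Elsewhere the plan is explicit about pairs. The primary objective (SAP 3.1) concerns two dose levels against placebo on liver fat. SAP 6.1 says "Pairwise comparisons of each active treatment group to control will be conducted vial linear contrasts", but that sentence belongs to the linear model for the primary endpoints. SAP 6.9.1 codes a contrast for each dose, for example "estimate 'JKB-121 5 mg : Placebo' TREATMENT -1 1 0", and promises estimates and intervals for each comparison.

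**The concern.** A secondary objective (SAP 3.2) is to establish a dose for later NASH studies, and another is to assess the effect on ALT. For a responder endpoint, both call for an answer for each dose against placebo. The coded analysis cannot give one. The general-association statistic asks whether the three arms differ in any way. The correlation statistic is a trend test on the codes 0, 1, 2. Either can be significant without a dose beating placebo, and the trend test can miss an active lower dose altogether. As no statistic is named, a reader of the output could also choose between lines that disagree.

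**Working it through.** There is no figure in the plan to reproduce here, because neither document gives a responder rate or a power for these endpoints. The check is of what the code produces.

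**Inputs.** From the SAP: three arms, about 60 subjects, 1:1:1, hence 20 per arm (6.1); stratification by diabetes status (4.2). From the protocol: two-sided 0.05 (13.2). Assumed: 10 subjects per arm in each stratum, and all responder counts and rates below.

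**Formulas.** In stratum s there are 30 subjects, 10 per arm, and c responders. Let k = c(30 − c)/29 and K the sum of k over strata. Let d be each arm's observed minus expected responders, summed over strata.
- General association (2 df): Q = 3·Σd²/K, with p = exp(−Q/2). Row mean scores gives the same value, because the response is binary.
- Correlation (1 df, scores 0, 1, 2): Q = (Σ score·d)²/(K·2/3).
- Pairwise CMH (1 df): squared sum of observed minus expected, divided by the sum of 10·10·r(20 − r)/(20²·19), where r is the responders in that pair and stratum.

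**Example 1: 2/8/2 responders of 20** (placebo, 5 mg, 10 mg; 1, 4, 1 in each stratum). K = 2 × 6 × 24/29 = 9.931; d = −2, 4, −2.
- General association: 3 × 24/9.931 = 7.25, p = 0.027.
- Correlation: 0 + 4 − 4 = 0, p = 1.00.
- 5 mg v placebo: r = 5 in each stratum, difference 1.5 + 1.5 = 3, variance 2 × 0.987 = 1.974; 9/1.974 = 4.56, p = 0.033. 10 mg v placebo: p = 1.00.

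The trend line shows nothing at all while one dose differs from placebo.

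**Example 2: 4/0/6** (2, 0, 3 in each stratum). K = 2 × 5 × 25/29 = 8.621; d = 0.667, −3.333, 2.667; Σd² = 18.667.
- General association: 3 × 18.667/8.621 = 6.50, p = 0.039.
- 5 mg v placebo: 2²/0.947 = 4.22, p = 0.040, with 5 mg worse. 10 mg v placebo: 1²/1.974 = 0.51, p = 0.48.

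The three-arm test is significant although neither dose beats placebo.

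**Example 3: 2/5/8** (1, 2, 4 and 1, 3, 4). K = 7 × 23/29 + 8 × 22/29 = 11.621; d = −3, 0, 3.
- General association: 3 × 18/11.621 = 4.65 on 2 df, p = 0.098.
- Correlation: 6²/7.747 = 4.65 on 1 df, p = 0.031.
- 5 mg v placebo: 1.5²/1.513 = 1.49, p = 0.22. 10 mg v placebo: 4.56, p = 0.033.

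Whether the result is significant depends on which printed line is read.

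**Rejection rates** by simulation at two-sided 0.05, two strata of 10 per arm, same rates in both strata (all rates assumed):

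| True rates, placebo/5 mg/10 mg | Correlation | General association | 5 mg v placebo | 10 mg v placebo |
|---|---|---|---|---|
| 10/45/10% | under 1% | about 78% | about 73% | about 4% |
| 10/10/45% | about 78% | about 78% | about 4% | about 73% |
| 10/25/40% | about 61% | about 49% | about 24% | about 62% |

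In the second row both three-arm tests do well but cannot say which dose is active. In the third row correlation and the 10 mg comparison have about the same power.

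**Does another section fill the gap?** The linear contrasts in SAP 6.1 do not reach a CMH test. The Hodges-Lehmann shift in the time-to-remission analysis is pairwise, but covers only subjects who remit, so it does not compare response rates. The Cox code there has no CLASS statement, so with codes 0, 1, 2 it too fits one linear dose term. No section supplies a dose-versus-placebo test for the responder endpoints.

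**The case against.** Several points on the other side stand.
- These endpoints are secondary in a trial that calls its objectives exploratory. Responder percentages will be shown by arm.
- Pairwise information on ALT itself is planned: SAP 6.9.2.2 applies the primary ANCOVA to ALT, AST and GGT at each visit, and the mixed-model code requests pairwise differences. A dose recommendation need not rest on a CMH p-value.
- The 10/45/10% pattern is close to the worst case for a trend statistic. In the monotone case little power is lost.
- SAP section 7 leaves table mock-ups to a separate document, to be final before database lock. A reader might infer that the choice of statistic is left until after unblinding. The documents do not show that; they show only that the SAP does not make the choice.

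A reader might also infer that the primary imputation analysis has the same gap, since Step 4 in SAP 6.9.1 says "The procedure PROC MIANALYZE would be used with estimated statistics" and names only least-squares means. The documents do not support that reading. Both contrasts are coded, results are promised for each comparison, and Step 3 compares each dose with placebo in every imputed data set. Step 4 omits the contrasts but does not exclude them. The difference of pooled arm means equals the pooled contrast. What a literal Step 4 would leave out is the contrast's standard error, interval and p-value.

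None of this supplies the missing responder comparison.

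**Conclusion.** The point holds for the secondary ALT responder endpoints in SAP 6.9.2.1. As coded they yield only three-arm statistics, with none designated, and no test, effect size or interval for either dose against placebo. That rests on the code and text alone. The size rests on assumed responder rates and equal strata: from almost total loss of power for the correlation test when only 5 mg works, to loss of attribution with little loss of power when response rises with dose.

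It would go too far to conclude that the trial cannot compare its doses with placebo. The primary objective (SAP 3.1) is about liver fat, and that comparison is properly specified. The change should be made, but it does not threaten the primary analysis.

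**What to change.** In SAP 6.9.2.1:
- Run the diabetes-stratified CMH twice, once on placebo and 5 mg and once on placebo and 10 mg, and name these as the comparisons of interest.
- For each, report a stratified risk difference with 95% confidence interval. With Mantel-Haenszel weights w = n₁n₀/(n₁ + n₀), Example 1 gives for 5 mg: difference 0.40 − 0.10 = 0.30; w = 5 per stratum; standard error √(2 × 25 × (0.024 + 0.009))/10 = 0.128; interval 0.30 ± 1.96 × 0.128, or 0.05 to 0.55.
- Give an exact stratified p-value when responders are few. This is a real prospect under the stricter definition: entry requires ALT above 40 U/L (women) or 60 U/L (men), and the limits of 20 and 30 U/L are half of those.
- Keep the three-arm test as supportive, and state which statistic is meant.

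In SAP 6.9.1, Step 4, add one sentence: the two ESTIMATE contrasts and their standard errors are pooled in PROC MIANALYZE along with the arm least-squares means.

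The cost is a WHERE clause, some extra output and the added sentence; no new data. It brings two unadjusted tests per endpoint, in line with the SAP's decision not to adjust for multiple comparisons. The change should be made before unblinding.

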### 6.9.2.2 Liver Function

The same descriptive statistics, ANCOVA model, and multiple imputation as the primary efficacy endpoint will be applied to serum aspartate aminotransferase (AST), ALT, and gamma-glutamyl transpeptidase (GGT) at each scheduled visit for the Full Analysis Set Population and the mITT Population.

As a sensitivity analysis, the change from baseline in AST, ALT, and GGT will be analyzed using a mixed-model repeated-measures (MMRM) ANCOVA model for the Full Analysis Set Population, implemented using SAS® Proc Mixed. The factors in the model will be diabetes stratum, treatment group, baseline value, visit, and the treatment group by visit interactions. An unstructured covariance matrix will be used (TYPE=UN). No imputation will be performed. The sample SAS code can be found below:

```
*****
Note:
  USUBJID = unique subject identifier
  TREATMENT = 0, (placebo), 1 (JKB-121 5 mg), 2 (JKB-121 10 mg)
  DIABSTAT = nondiabetic, diabetic
  VISIT = visit
  BASE = baseline value
  CHG = change from baseline to the specified visit
*****;
proc mixed;
  class USUBJID DIABSTAT TREATMENT BASE VISIT;
  model CHG = DIABSTAT TREATMENT BASE VISIT TREATMENT*VISIT;
  Repeated VISIT / TYPE=UN sub=USUBJID;
  lsmeans VISIT*TREATMENT / cl pdiff slice=VISIT;
run;
```

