### 3.2 Secondary Objectives

The secondary objectives are:

- Determine the pharmacokinetic profile of JKB-121 in nonalcoholic steatohepatitis (NASH)
- Assess the impact of treatment with JKB-121 on metabolic markers
- Assess the impact of treatment on liver enzymes (serum alanine aminotransferase [ALT]) over 24 weeks.
- Establish the recommended dose for future NASH treatment studies.
- To evaluate changes of NASH related biomarkers such as adiponectin, leptin, ghrelin, tumor necrosis factor alpha (TNF-alpha), TGF-beta, hyaluronic acid and matrix metalloproteinase 2 (MMP-2).

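### SAP 6.9.2.2 defines no continuous ALT treatment difference that combines visits, and the MMRM that could supply one fits baseline ALT as a category

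*SAP*

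**What the plan says.** - **Objective.** SAP 3.2 and protocol 5.1.2: "Assess the impact of treatment on liver enzymes (serum alanine aminotransferase [ALT]) over 24 weeks".
- **Visits.** Protocol 10.4 draws chemistry including ALT at Weeks 2, 4, 8, 12, 16, 20 and 24 on treatment.
- **Continuous ALT.** The protocol synopsis lists the Week 24 change first under liver function. SAP 5.2 lists the change at every scheduled visit. SAP 6.9.2.2 applies the primary ANCOVA with multiple imputation to AST, ALT and "gamma-glutamyl transpeptidase (GGT) at each scheduled visit for the Full Analysis Set Population and the mITT Population".
- **Endpoints that use several visits.** SAP 5.2 and 6.9.2.1 define remission, time to remission, a normal value at any time in an interval, and a 20% fall at any time. For example: "A subject who had as two consecutive ALT values within normal range during the treatment period will be defined as a responder".
- **Repeated-measures model.** SAP 6.9.2.2 plans an MMRM with unstructured covariance as a sensitivity analysis. Its only output request is "lsmeans VISIT*TREATMENT / cl pdiff slice=VISIT". The CLASS statement includes `BASE`, and the text counts baseline value among the factors.
- **Power.** SAP 6.1: "The current sample size of 20 subjects per group should yield approximately 73% power to detect a treatment effect of at least 30 U/L". The SD behind this figure rests on two inputs, "derived assuming SDs of 40 for the pre-and post-baseline measurements with a correlation of 0.25".

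**The concern.** The objective concerns a period, but the plan answers it either with threshold endpoints or with a row of single-visit tests. The one model that holds all the visits is not asked for a summary across them. With 20 patients per arm, a single-visit contrast carries the full visit-to-visit noise of ALT, and averaging late visits could reduce that noise without new data. The SAP's endpoint list does not single out Week 24, so several ALT p-values per dose would be on the table with no multiplicity rule. A further objective is to recommend a dose, so it matters which ALT figure is read.

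The coding of baseline is a separate fault in the same model. As written, the MMRM could not give a precise treatment difference of any kind, averaged or not.

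**Working it through.** **1. The plan's own figure.** The SD of the change is 40 × √(2 × (1 − 0.25)) = 49.0, which the SAP rounds to 50 (it once calls this an SE). For an unpaired t-test with 20 per arm, the noncentrality is (30/50) × √(20/2) = 1.90 on 38 df, and two-sided 5% power is 46% (47% with SD 49.0). The stated 73% does not reproduce. A one-sample test of change within one arm of 20 gives 72% to 74%, but that is not the test named. The 73% is not used below.

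**2. Week 24 alone, by the planned ANCOVA.** The residual SD is 40 × √(1 − 0.25²) = 38.7. The error df are 60 − 5 = 55 (intercept, two treatment terms, stratum, baseline). The noncentrality is (30/38.7) × √10 = 2.45, and power is **67%**.

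**3. Mean of Weeks 16, 20 and 24.** Let r be the correlation between on-treatment visits. The documents do not give it, so 0.25 to 0.9 is assumed. With complete data, the residual variance of the three-visit mean given baseline is

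1600 × (1 + 2r)/3 − (0.25² × 1600) = 1600 × (1 + 2r)/3 − 100.

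Two time courses are assumed, because the plan gives none:
- the full 30 U/L is present by Week 16, so the mean effect is 30;
- the effect grows linearly to 30 U/L at Week 24, so the mean effect is 30 × (16 + 20 + 24)/(3 × 24) = 25 U/L.

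| r | Residual SD | Power, full effect by Week 16 | Power, linear growth |
|---|---|---|---|
| 0.25 | 26.5 | 94% | 84% |
| 0.5 | 31.1 | 85% | 70% |
| 0.7 | 34.4 | 77% | 62% |
| 0.8 | 35.9 | 74% | 58% |
| 0.9 | 37.3 | 70% | 55% |

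Against 67% for Week 24 alone, the first case gains 27 points at r = 0.25 and 3 at r = 0.9. The second runs from a gain of 16 points to a loss of 12.

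**4. Baseline in CLASS.** With baseline continuous, 55 between-subject df remain. With `BASE` in CLASS, each distinct baseline ALT value takes its own parameter. If 60 patients have D distinct values, about 60 − D − 3 = 57 − D df remain (two treatment terms and one stratum term also come off). A patient whose baseline value nobody shares then adds nothing to the between-arm comparison. In a simulation of 60 patients with an assumed baseline mean of 90 and SD of 40 U/L, about 10 df remained, which corresponds to D of about 47. The PROC GLM code in SAP 6.9.1 does not have this fault: its CLASS statement holds only treatment and diabetes stratum.

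**The case against.** Several counter-arguments carry weight.

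- **The repeated data are not thrown away.** A reader might infer that they are. The MMRM uses every visit, and PROC MIXED by default prints a Type 3 treatment test averaged over visits. This stands, so the gap is narrow. That test has 2 df across three arms, gives no dose-versus-placebo estimate or interval, and is not designated by the SAP.
- **A continuous ALT answer is named.** The protocol synopsis lists the Week 24 change, and the objective can fairly be read as change from baseline to Week 24. This stands, and it is why Week 24 should lead. Week 24 against an average of visits is a choice of estimand, and neither is an error.
- **A power gain cannot be presented as following from the plan's own inputs.** This stands too. It needs a between-visit correlation and a time course, and the documents give neither. If the effect is still growing and visits correlate highly, averaging loses power.
- **A Week 16 to 24 window is not literally 24 weeks.** True, but averaging from the start is riskier. With linear growth, the mean effect over Weeks 4 to 24 is 30 × 14/24 = 17.5 U/L, and ANCOVA power falls to 47%, 37% and 34% at r = 0.5, 0.7 and 0.8.
- **More contrasts in an unadjusted plan.** This is a fair caution for an exploratory phase II trial, and the reason to label the added contrast supportive.

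Step 3 of the imputation procedure in SAP 6.9.1 averages Weeks 12 and 24. SAP 6.9.2.2 does not say whether that carries over to ALT, so it cannot be counted as a defined ALT summary.

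**Conclusion.** The point holds in a limited form. The SAP defines no continuous dose-versus-placebo ALT estimate that combines visits, and the MMRM that could supply one is coded with baseline as a category. The coding fault is clear from the text. Its size, about 10 of 55 between-subject df left, depends on how many patients share a baseline value.

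The value of a late-visit average is conditional. Relative to 67% at Week 24, it ranges from a gain of about 27 points to a loss of about 12 over the assumed correlations (0.25 to 0.9) and two time courses, with complete data. The change is worth making because it is cheap and fixes in advance which continuous ALT summaries will be read. The documents do not support a claim that ALT data are wasted or that a given power gain is being forgone.

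**What to change.** In SAP 6.9.2.2:

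1. Remove `BASE` from the CLASS statement and describe baseline as a continuous covariate in the text.
2. Name the Week 24 ALT change, as in the protocol synopsis, as the lead continuous ALT contrast for each dose.
3. Pre-specify one added MMRM contrast per dose: the equally weighted mean of the dose-minus-placebo differences at Weeks 16, 20 and 24, with a 95% CI. Label it a supportive continuous summary. It takes one ESTIMATE statement per dose on `TREATMENT` and `TREATMENT*VISIT`.
4. If a power gain is mentioned, state the assumed between-visit correlation and time course beside it.

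The cost is a few lines of SAP text and code in a model already planned, with no new data or visits. The downside is one more unadjusted contrast per dose, which will understate the Week 24 effect if that effect is still growing. Keeping Week 24 as the lead covers this.

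### The liver-enzyme MMRM has no baseline-by-visit term, so it adjusts for baseline differently from the visit-by-visit ANCOVA it is meant to check; BASE must first come out of CLASS

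*SAP*

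**What the plan says.** SAP 6.9.2.2 first applies the primary ANCOVA model, with multiple imputation, to each enzyme "at each scheduled visit for the Full Analysis Set Population and the mITT Population". The code for that model, in SAP 6.9.1, has "class TREATMENT DIABSTAT" as its class statement. BASE is therefore a continuous covariate there, and each visit's fit has its own baseline slope.

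The check on it is described thus: "As a sensitivity analysis, the change from baseline in AST, ALT, and GGT will be analyzed using a mixed-model repeated-measures (MMRM) ANCOVA model". It uses an unstructured covariance and no imputation. In prose: "The factors in the model will be diabetes stratum, treatment group, baseline value, visit, and the treatment group by visit interactions". In code, the class statement is "class USUBJID DIABSTAT TREATMENT BASE VISIT" and the model statement is "model CHG = DIABSTAT TREATMENT BASE VISIT TREATMENT*VISIT". Treatment interacts with visit in both places; baseline does not in either.

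The only information on how enzyme values relate to baseline is in SAP 6.1, where the ALT standard deviation of change is derived "assuming SDs of 40 for the pre-and post-baseline measurements with a correlation of 0.25". That correlation is not tied to a visit.

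**The concern.** When standard deviations are equal, the slope of change on baseline is r − 1, where r is the correlation of that visit's value with baseline. If early values track baseline more closely than late ones, the right slope differs by visit. A single slope is then a compromise pulled towards the early visits, and it adjusts Week 24 poorly.

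Two things are at stake. The first is interpretation: the MMRM is useful because it treats missing data differently from the imputed ANCOVA. If it also adjusts differently for baseline, a disagreement between the two cannot be put down to missing data alone. The second is precision at Week 24, with 20 subjects per arm and no allowance for dropout.

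**Working it through.** **Inputs from the documents.** 20 per arm; SD 40 U/L before and after treatment; r = 0.25 (SAP 6.1). ALT is drawn at Weeks 2, 4, 8, 12, 16, 20 and 24 (Protocol 10.4), so seven visits are used.

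**Inputs assumed.** The correlation with baseline at each visit, the correlations between post-baseline visits, and complete data.

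**1. The plan's own figure.** SD of change = √(2 × 40² × (1 − 0.25)) = √2400 = 48.99, which agrees with the plan's 50. The 73% power quoted beside it does not follow from these inputs (about 46% by t, 47% by the normal approximation). That is a separate matter and is not used below.

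**2. The code as written.** With BASE in CLASS, the model has one parameter per distinct baseline value.
- With 60 simulated integer ALT baselines (SD 33–36, 200 samples for each of two distributions) there were about 39–51 distinct values.
- Relative to the visit-specific ANCOVA, the Week 24 contrast kept a median 45–52% of the information (5th to 95th percentile about 25–68%).
- If all baselines are distinct, each level identifies one subject and the contrast cannot be estimated.

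**3. BASE continuous, one common slope.** Let **r** be the vector of correlations with baseline, **R** the correlation matrix of the post-baseline visits, and **S** = **R** − **rr**′. Under an unstructured covariance the common slope, on the correlation scale, is

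b = **1**′**S**⁻¹**r** / **1**′**S**⁻¹**1**.

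Put d = b − r₂₄. The Week 24 residual variance is 1600 × (1 − r₂₄²) with visit-specific slopes and 1600 × (1 − r₂₄² + d²) with a common slope, so

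variance ratio = 1 + d² / (1 − r₂₄²).

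For r₂₄ = 0.25 the visit-specific variance is 1600 × 0.9375 = 1500.

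**4. Results**, with r falling linearly by visit:

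| r, Week 2 to Week 24 | Between-visit correlation | d | Ratio |
|---|---|---|---|
| constant 0.25 | any | 0 | 1.00 |
| 0.60 to 0.25 | AR(1) 0.7 | 0.207 | 1.05 |
| 0.60 to 0.25 | AR(1) 0.9 | 0.239 | 1.06 |
| 0.60 to 0.25 | exchangeable 0.5 | 0.275 | 1.08 |
| 0.60 to 0.25 | exchangeable 0.6 | 0.308 | 1.10 |
| 0.80 to 0.50 | AR(1) 0.7 | 0.185 | 1.05 |
| 0.80 to 0.50 | exchangeable 0.6 | 0.288 | 1.11 |
| 0.75 to 0.25 | AR(1) 0.7 | 0.333 | 1.12 |
| 0.75 to 0.25 | AR(1) 0.9 | 0.432 | 1.20 |
| 0.75 to 0.25 | exchangeable 0.5 | 0.568 | 1.34 |
| 0.75 to 0.25 | exchangeable 0.6 | 0.723 | 1.56 |

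Example: 1 + 0.432² / 0.9375 = 1 + 0.187 / 0.9375 = 1.20.

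**5. What 1.20 means.** The effective size is 20 / 1.20 = 16.7 per arm. For a 30 U/L difference, power = Φ(30 / (SD × √(2/20)) − 1.96). SD √1500 = 38.7 gives 69%; SD √1800 = 42.4 gives 61%.

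**6. Cross-check by simulation.** In 1,500 complete-data trials per scenario at 20 per arm, the ratios were 1.20 (0.75 to 0.25), 1.07 (0.60 to 0.25), 1.07 (0.80 to 0.50) and 0.99 (constant 0.5). Type I error was about 5% with either model.

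**The case against.** The strongest reply is that the cost of a common slope belongs to a model the SAP does not contain. The class statement makes BASE categorical, and the prose lists baseline among the factors. This stands as to order and emphasis: the CLASS entry is the larger fault. But correcting it alone leaves one slope for all visits, so the missing term still needs its own line.

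Second, no document says that the correlation with baseline declines. This stands. With 0.25 at every visit the loss is zero, and every figure above that is conditional.

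Third, the size depends on inputs the plan leaves open. Between-visit correlations alone move the steep case from 1.12 to 1.56. The SAP does not name the visits in the MMRM: the protocol synopsis lists Weeks 4 to 24 for these enzymes, and chemistry is also drawn at Week 28. Dropping Week 2 in the steep case (decline linear in weeks, AR(1) 0.9) lowers the ratio from 1.21 to 1.16. This stands, and it is why a range is given.

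Fourth, this is sample code for a sensitivity analysis of secondary endpoints in an exploratory trial. The main ALT analysis is untouched, and no difference in estimates has been shown under dropout. This also stands and limits the point to a cheap improvement.

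A reader might go further and infer that the program as printed imposes a common slope, that the loss has a fixed ceiling such as one sixth, or that the MMRM's p-values are invalid. The first is contradicted by the class statement. The second fails because the ratio passes 1.20 under equally arbitrary assumptions; with decline linear in weeks and exchangeable 0.6 it reaches 1.73. The third is contradicted by the simulated type I error.

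**Conclusion.** The point holds as a minor one. The MMRM keeps the baseline effect constant over visits and the analysis it checks does not, so the two differ in more than their treatment of missing data. As printed, the class declaration of BASE is the more serious fault: on simulated baselines it loses about half the Week 24 information, or leaves the contrast not estimable.

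With BASE continuous, the Week 24 variance inflation is nil under constant correlation, roughly 5–10% under mild decay and roughly 10–50% under steep decay. These figures rest on equal standard deviations, complete data, seven visits and assumed correlations. They are illustrations, not bounds.

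**What to change.** In SAP 6.9.2.2, in this order:

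1. Remove BASE from the CLASS statement and describe baseline in the text as a continuous covariate.
2. Add `BASE*VISIT` to the MODEL statement and a baseline-by-visit interaction to the text.

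The order matters. Adding the interaction while BASE is still a class variable would give every baseline level its own parameter at every visit and make the model worse.

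It would also help to name the visits that enter the model and to consider `DIABSTAT*VISIT`, since the diabetes effect is likewise held constant here but free at each visit in the ANCOVA.

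The cost is a two-line edit. With seven visits the interaction uses 6 degrees of freedom (7 − 1), and about 1% in variance if the slope really is constant (simulated ratio 0.99). In return, the MMRM and the ANCOVA share the same baseline adjustment and differ mainly in how they handle missing data.
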